4 INVESTIGATIONAL PLAN

4.1 Overall Study Design and Plan

Study M20-370 is a randomized, double-blind, placebo-controlled, multicenter, 52-week Phase 2 study to assess the safety, tolerability, efficacy, PK, PD, and immunogenicity following multiple subcutaneous (SC) injections of ABBV-154 or placebo in 160 subjects with glucocorticoid-dependent PMR, as defined in Section 5.1.

The Screening Period may be up to 35 days. At the Baseline Visit, subjects will be randomized to one of 4 treatment arms in a 1:1:1:1 ratio, as follows: placebo administered SC in combination with a glucocorticoid taper or ABBV-154 administered as 40 mg every other week (EOW), 150 mg EOW, or 340 mg EOW in combination with a glucocorticoid taper. The glucocorticoid taper is identical for placebo and active treatment groups. Starting at Baseline, each subject will switch from oral glucocorticoids obtained from independent sources to oral prednisone/prednisolone provided by the Sponsor at the equivalent dose that the subject was taking just prior to the Baseline Visit, rounded up to the nearest 1 mg to a maximum of 15 mg. Beginning at Week 3, subjects will taper prednisone/prednisolone per the protocol-defined glucocorticoid taper schedule to 0 mg by Week 24 and remain off prednisone/prednisolone until the end of the Treatment Period, Week 52, unless a PMR flare is confirmed. A safety follow-up visit will be performed approximately 70 days after the last administration of ABBV-154/placebo.

If a subject has a suspected PMR flare at any time during the study, the flare should be confirmed according to the protocol-defined flare definition as soon as possible, prior to initiating glucocorticoid rescue treatment. Flare may be confirmed at either a scheduled visit or unscheduled visit. PMR must be confirmed as the cause of flare by eliminating other causes of the subject's symptoms/signs such as infection or other underlying disease. Once flare is confirmed at the visit, glucocorticoid rescue can be administered with the dose and subsequent tapering at the discretion of the investigator, taking into consideration local standard of care, the subject's preflare and/or baseline dose, and not exceeding 15 mg/day.

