Starting at the Baseline Visit, all subjects will switch from oral glucocorticoids obtained from independent sources to open-label oral prednisone/prednisolone provided by the sponsor at the same dose they were taking just prior to the Baseline Visit, rounded up to the nearest 1 mg to a maximum of 15 mg. At the Baseline Visit (Day 1), the subject may take non-sponsor provided oral glucocorticoid at the required dose prior to randomization so that the subject does not have to delay the usual time of glucocorticoid dosing. If a subject has already taken the glucocorticoid dose at home on the day of the Baseline Visit, dosing should not be repeated with sponsor-provided prednisone/prednisolone. Open-label prednisone/prednisolone will be self-administered orally (PO) once per day (QD) (Table 2). The baseline dosage will be administered QD until the Week 3 visit, at which time tapering will begin as described in Section 6.1 of the Operations Manual (Appendix H). Glucocorticoids should be stored as specified on the label (may differ by manufacturer and local requirements) in a secure location.

Table 2. Non-Investigational Product

Study Drug	Dosage Form	Strength	Route of Administration	Manufacturer
Prednisone/ Prednisolone	Tablets	1 mg, 5 mg, and 10 mg	Oral	Generic ^a

a. Prednisone/prednisolone may be supplied by AbbVie per local requirements.

If a subject or home health nurse (if utilizing home care visits) is unable to come to the study site to pick up their study drug due to COVID-19 or other reasons, a direct-to-patient study drug shipment can be made from the study site to the subject if allowed by local regulations. AbbVie will submit any required notifications to the regulatory authority as applicable.

Subjects will be instructed to return all drug containers (even if empty) to the study site personnel at each study visit; study site personnel will document compliance.

Glucocorticoid Tapering Schedule

Starting at Week 3, prednisone/prednisolone will be tapered to 0 mg prednisone/prednisolone per day according to the schedule in Section 6.1 of the Operations Manual (Appendix H), based on the glucocorticoid dosage at Baseline. The glucocorticoid taper will be completed by Week 24 for all subjects.

Rescue Treatment for PMR Flare

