7.4 Statistical Analyses for Efficacy

Efficacy analysis will be performed by the subject's randomized treatment group. All statistical tests will be performed at a 2-sided significance level of 0.1. A 95% confidence interval (CI) of the treatment difference between each ABBV-154 dose and placebo will be provided. The actual value of stratification factors will be used in the analysis. Enrollment in the optional PK sampling is not expected to impact any of the efficacy endpoints and will thus not be used as a stratification factor in the analysis.

- For time-to-event endpoints, comparison of number of events will be made between each ABBV-154 dose and placebo based on log-rank test stratified by stratification factors. The point and CI estimate of median time to event and event-free rate for each group will be reported based on Kaplan-Meier curves. Hazard ratio and its corresponding CI for each ABBV-154 group compared with placebo will be estimated using Cox regression analysis adjusting for stratification factors. For all analyses of time-to-event endpoints, subject without an event at the time of the analysis will be administratively censored at the time of the last available assessment.
- For categorical variables, pairwise comparison will be made between each ABBV-154 dose and placebo using the Cochran-Mantel-Haenszel (CMH) test, adjusting for stratification factors. Nonresponder imputation incorporating multiple imputation (NRI-MI) to handle COVID-19 will be the primary approach to handle missing data for categorical endpoints.
- For continuous variables other than glucocorticoid dose, the comparison will be made between each ABBV-154 dose and placebo based on the mixed effect model repeated measures (MMRM) adjusting for visit, interaction between treatment and visit, actual values of stratification factors as fixed factors, and baseline value as a covariate. The MMRM will be the primary approach to handle missing values for continuous endpoints.
- For analyses of glucocorticoid dose, comparison will be made between each ABBV-154 dose and placebo based on the analysis of covariance (ANCOVA) adjusting for stratification factors as fixed factors, and baseline glucocorticoid dose as a covariate.

Summary and Analysis of the Primary Endpoints

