## 2.4 Sample Size Determination

A total of 37 flares in the highest dose of ABBV-154 group and placebo group would provide more than 90% power to detect a hazard ratio of 0.296 at 2-sided significance level of 0.1. The hazard ratio of 0.296 is determined under the assumption that flares would occur during the tapering and within 12 weeks after the end of tapering (up to Week 36), and 70% and 30% of subjects will remain flare-free by Week 36 in the highest dose of ABBV-154 group and placebo group, respectively.

Based on an  $E_{\max}$  model with  $ED_{50}$  of 150 mg, a total of 74 flares are expected for the Primary Analysis. A sample size of 40 subjects in each of the ABBV-154 and placebo arms is planned to ensure appropriate accrual of flares. A sample size re-estimation may be considered at an interim analysis prior to unblinding of the study team. The sample size increase will be capped at approximately 100 subjects.

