placebo. Note that measurements will be considered as missing after the start of confounding medication before MI. Regardless of MI imputed values, subjects after receiving confounding medication will be counted as non-responders.

Efficacy assessments after the initiation of rescue medication, immunomodulator or violation of protocol-allowed systemic glucocorticoid use will not be included in the analyses. As a result, the subjects will be considered as non-responders in the NRI-MI approach.

- **Mixed-Effect Model Repeat Measurement (MMRM):** MMRM will be the primary approach to the analysis of continuous variables except for glucocorticoid dose. The repeated measures analysis will be conducted using a mixed model including observed measurements at all visits. Subject's observations after intercurrent events will not be used in the MMRM. The mixed model includes the categorical fixed effects of treatment, visit and treatment-by-visit interaction, stratification factors at randomization [Glucocorticoid use at Baseline ( $\geq 10$  mg/day;  $< 10$  mg/day prednisone equivalent); Length of prior glucocorticoid treatment for PMR ( $\leq 1$  year;  $> 1$  year)], and the continuous fixed covariates of baseline measurement. An unstructured variance-covariance matrix (UN) will be used. If the model does not converge, an alternative variance-covariance structure matrix (e.g., autoregressive (1) or compound symmetry) will be used. Parameter estimation is based on the assumption of data being missing at random and the method of restricted maximum likelihood (REML) will be used.
- **Analysis of covariance (ANCOVA):** ANCOVA will be the primary approach for the analysis of glucocorticoid dose. No intercurrent event will be considered in the analysis of glucocorticoid dose. The ANCOVA model includes the categorical fixed effects of treatment and stratification factors at randomization [Glucocorticoid use at Baseline ( $\geq 10$  mg/day;  $< 10$  mg/day prednisone equivalent); Length of prior glucocorticoid treatment for PMR ( $\leq 1$  year;  $> 1$  year)], and baseline glucocorticoid dose as a covariate.
- **As Observed (AO):** The AO analysis will not impute values for missing evaluations, and thus a subject who does not have an evaluation on a scheduled

visit will be excluded from the AO analysis for that visit. AO will include all values collected in the study.

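### The ANCOVA for the two glucocorticoid-dose secondary endpoints does not say whether it is four-arm or pairwise and allows only one residual variance; read as four-arm, it makes the 40 mg versus placebo standard error modestly too small under the plan's own flare assumptions

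*SAP*

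**What the plan says.** Two of the three secondary endpoints are glucocorticoid-dose measures (SAP 3.2). SAP 9.2.2 makes ANCOVA their primary analysis: "The ANCOVA model includes the categorical fixed effects of treatment and stratification factors at randomization", plus baseline dose as a covariate. Protocol 7.4 sets the contrasts: "For analyses of glucocorticoid dose, comparison will be made between each ABBV-154 dose and placebo based on the analysis of covariance (ANCOVA"), each at the level given by "All statistical tests will be performed at a 2-sided significance level of 0.1", with a 95% CI. Neither document says whether one four-arm model or three two-arm models are fitted. The MMRM in the same SAP section has a stated covariance structure and a fallback; the ANCOVA has neither. SAP 9.4.3 plans no sensitivity analysis for secondary endpoints.

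Three other provisions determine where the residual spread comes from:
- Protocol 5.8: "The glucocorticoid taper will be completed by Week 24 for all subjects". Protocol 4.1 makes the taper the same in every arm.
- SAP 9.2.2: "No intercurrent event will be considered in the analysis of glucocorticoid dose". Rescue doses therefore count. Protocol 5.8 leaves them to the investigator, up to 15 mg/day.
- SAP 2.4 assumes that "70% and 30% of subjects will remain flare-free by Week 36" (340 mg and placebo respectively), with an Emax curve, ED50 150 mg, across doses.

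**The concern.** An ordinary ANCOVA estimates one residual variance for all arms in the model. Given baseline dose, an adherent subject without a flare has a scheduled Week 24 dose of 0 mg and a taper total fixed by the schedule. Most residual spread therefore depends on who flares, when, and how much rescue is given. If the higher doses prevent flares as planned, their dose data vary less than those on placebo and 40 mg. In a four-arm fit, the quieter arms lower the pooled variance that is then applied to 40 mg versus placebo.

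At stake are the p-value and interval for the lowest dose on two of three secondary endpoints. No overall type I control is planned (SAP 13.0), so the per-comparison 0.1 level is the only error statement these tests carry.

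**Working it through.** **Inputs from the documents.** 40 per arm ("A sample size of 40 subjects in each of the ABBV-154 and placebo arms is planned"); 1:1:1:1 allocation; 2-sided alpha 0.1; 95% CIs; flare-free at Week 36 of 0.30 (placebo) and 0.70 (340 mg); Emax with ED50 150 mg.

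**Assumptions not in the documents.** Constant flare hazard to Week 36; linear taper from Week 3 to Week 24 (the schedule is in an Operations Manual section not supplied); baseline dose spread over 5-15 mg; several rescue-dose patterns; no dropout. These are modelling inputs only.

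**1. The plan's own figure.** HR = ln 0.7 / ln 0.3 = 0.296. With 37 flares, Schoenfeld power = Φ(√(37/4) × |ln 0.296| − 1.645) = Φ(3.70 − 1.645) = 98%, which agrees with the stated more than 90%. The documents give no SD or power for the dose endpoints.

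**2. Flare rates by arm.** Emax coefficient = 0.4 × 490/340 = 0.5765. Flare-free at Week 36 is 0.3 + 0.5765·d/(150 + d), that is 0.300 / 0.421 / 0.588 / 0.700 for placebo / 40 / 150 / 340 mg. With constant hazard from Day 1, the proportion flared by Week 24 is 1 − (flare-free)^(24/36) = 0.552 / 0.438 / 0.298 / 0.212.

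**3. Closed form, Week 24 dose.** Let the dose be 0 without flare, with mean m and SD s after flare. Then V(p) = p·s² + p(1 − p)·m². With equal arms the pooled variance is the mean of the four V. For 40 mg versus placebo, r = model SE / true SE = √(pooled V / mean of the two arms' V). The rejection rate under no difference is 2[1 − Φ(1.645r)], and coverage is 2Φ(1.96r) − 1.

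| Case | s | V/m² (placebo, 40, 150, 340) | r | Result |
|---|---|---|---|---|
| Planning curve, 40 mg active | 0 | 0.247, 0.246, 0.209, 0.167 | 0.94 | coverage 93.4% |
| Planning curve, 40 mg active | m/2 | 0.385, 0.356, 0.284, 0.220 | 0.92 | coverage 92.7% |
| 40 mg inactive, others as planned | 0 | 0.247, 0.247, 0.209, 0.167 | 0.94 | rejects 12.3% |
| 40 mg inactive, others as planned | m/2 | 0.385, 0.385, 0.284, 0.220 | 0.91 | rejects 13.5% |

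The same ratio for 340 mg versus placebo is 1.01-1.03.

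**4. Cumulative dose.** No simple closed form applies. One simulated rescue pattern gives residual SDs of 338 / 339 / 276 / 242 mg (40 mg inactive). Pooled SD = √[(338² + 339² + 276² + 242²)/4] = 302 mg against about 338.5 mg in the two arms compared, so r = 0.89 and the implied rejection rate is 14%. The simulation itself gave r = 0.91 and 13.1%.

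**5. Simulation (3,000 trials per setting, Monte Carlo SE about 0.006), 40 mg inactive, nominal 10%.**

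| Analysis | Week 24 change | Cumulative dose |
|---|---|---|
| Four-arm, pooled variance | 11.5-14.5% | 13.1-16.0% |

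Across both endpoints, four-arm HC3 gave 8.3-10.3% and separate two-arm fits gave 8.8-10.8%.

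The 16% is the upper end over all settings. Other runs with different rescue, taper and hazard inputs gave lower values, including 11.1% and 12.7% in one base case. A fair overall range is 11-15%. Under the planning rates, model SE over true SE was 0.92-0.96 (Week 24 change) and 0.89-0.94 (cumulative dose), coverage 91-93%, and HC3 restored about 95%.

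**6. Where the effect is absent or reversed.**
- All doses inactive: 10.0% and 10.6%.
- Week 36 flare rates already reached by Week 24: 9.4-11.7% in closed form (s from 0 to 5 mg) and 9.5-10.5% by simulation for Week 24 change; 11.2-12.8% for cumulative dose.
- Week 36 flare rates 0.95 / 0.95 / 0.70 / 0.60: 6.4% for Week 24 change (conservative) and 10.9% for cumulative dose.
- Half the planned effect at 340 mg: 10.3-10.7% and 10.8%.

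**The case against.** The strongest reply is that the documents never state a four-arm fit. Protocol 7.4 and SAP 9.4.2 describe each dose against placebo, and with separate equal-sized pairs the problem largely goes away. That stands. A single model with a categorical treatment effect is the natural reading of SAP 9.2.2, but the text allows either, and the two give different standard errors.

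A reader might infer that the spread differs between arms by design, so that the test never holds its 0.1 level. The documents do not support this: the taper is identical in all arms, and spread differs only if the higher doses prevent flares. The 11-15% figure also requires an inactive 40 mg arm, whereas the plan's Emax curve gives 40 mg some effect. In the planning case the defect is an interval that is too narrow, not a false positive.

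A reader might also infer that dose selection would be misled. No decision rule in the documents uses this ANCOVA. The minimum effective dose comes from MCP-Mod on the primary endpoint (SAP 9.6).

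Other sources of spread were left out of the main simulations: SAP 9.4.1 counts all systemic glucocorticoid use whatever the indication, and dosing after study-drug discontinuation is free. With an assumed 15% of subjects per arm having such use, rejection was 10.7-11.4% for Week 24 change and 11.4-12.8% for cumulative dose. This dilutes the effect but does not remove it for cumulative dose.

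**Conclusion.** The point holds as a modest, conditional defect and a gap in specification. If SAP 9.2.2 is run as one four-arm ANCOVA and the planning flare rates apply, the 40 mg versus placebo standard error is about 4-11% too small and the 95% CI covers about 91-93%. If 40 mg is inactive while the higher doses work as planned, nominal 10% becomes roughly 11-15%. The effect is larger and more consistent for cumulative dose; for Week 24 change it can be close to zero or reverse. The comparison of 340 mg with placebo is hardly affected (SE ratio 0.99-1.06). The sizes rest on assumed rescue patterns, taper shape and flare hazard, none of which the supplied documents give. These are secondary endpoints in a Phase 2 trial, so the case for acting is that the correction is cheap and works in either direction.

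**What to change.** In the ANCOVA bullet of SAP 9.2.2, state that one four-arm model is fitted with the present terms, and that standard errors, p-values and confidence intervals for both glucocorticoid-dose endpoints use the HC3 heteroscedasticity-consistent variance. Point estimates stay the same.

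Two alternatives are acceptable if preferred: a separate two-arm model for each dose against placebo, or arm-specific residual variances in a mixed model with Satterthwaite degrees of freedom. Neither is equivalent to HC3. Both may shift the adjusted estimates slightly, the first because the covariate coefficients are re-estimated in each pair and the second because it reweights subjects. The arm-specific variance was not checked for size here.

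The cost is one sentence and a small change in code. The apparent chance of significance for 40 mg falls by about 4-6 points under the planning assumptions (for example from about 25% to 20% for Week 24 change), because the higher figure relies on a standard error that is too small. For 340 mg, power changes by at most about 2 points. No change to design, data collection or clinical conduct follows.

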### **9.3 Primary Efficacy Endpoint(s) and Analyses**

#### **9.3.1 Primary Efficacy Endpoint(s)**

The primary endpoint is the time to flare, where flare is defined as follows:

- Presence of clinical signs and symptoms of PMR
- AND
- Requirement to increase the glucocorticoid dose per investigator.

Clinical signs and symptoms of PMR are defined as shoulder and/or hip girdle pain with inflammatory stiffness, neck pain with inflammatory stiffness, or new or worsened limited range of motion of hips and/or shoulders, as outlined in protocol.

#### **9.3.2 Main Analysis of Primary Efficacy Endpoint(s)**

The statistical null hypothesis corresponding to the primary endpoint is that there is no difference between an ABBV-154 group and the placebo group in time to flare.

Analysis of the primary endpoint will be conducted in the ITT Population based on treatment as randomized. Comparison of the primary endpoint will be made between each ABBV-154 group and the placebo group using logrank test stratified by baseline stratification factors [Glucocorticoid use at Baseline ( $\geq 10$  mg/day;  $< 10$  mg/day prednisone equivalent); Length of prior glucocorticoid treatment for PMR ( $\leq 1$  year;  $> 1$  year)].

The attributes of the estimands corresponding to the primary efficacy endpoint are summarized in Table 1.

**Table 1. Summary of the Estimand Attributes of the Primary Efficacy Endpoint(s)**

Estimand Label	Attributes of the Estimand				Statistical Summary
	Treatment	Endpoint	Population	Handling of Intercurrent Events (IE)	
Primary: Time to flare (Composite)	ABBV-154 vs. Placebo	Time to flare	ITT	IE1: at the time of immunomodulator initiation  IE2: at the time of violation of protocol-allowed systemic glucocorticoid use  Subjects will be censored at the time of intercurrent event.	Between ABBV-154 and placebo: difference in number of events, difference in median time to event, event-free rate difference, hazard ratio and its corresponding CI

**9.3.3 Sensitivity and Supplementary Analyses of the Primary Efficacy Endpoint(s)**

Not applicable.

**9.4 Secondary Efficacy Endpoints and Analyses**

**9.4.1 Secondary Efficacy Endpoints**

The categorical secondary endpoint is

- Achievement of flare-free state up to Week 24

The continuous secondary endpoints are

- Cumulative glucocorticoid dose by 24 weeks

- Change from Baseline in glucocorticoid dose at Week 24

For the analysis of glucocorticoid dose, all systemic glucocorticoid use will be included regardless of the indication.

#### **9.4.2 Main Analyses of Secondary Efficacy Endpoints**

The statistical null hypothesis corresponding to the secondary endpoint is that there is no difference between an ABBV-154 group and the placebo group.

Analysis of the secondary endpoint will be conducted in the ITT Population based on treatment as randomized. Comparison of the secondary endpoint will be made between each ABBV-154 group and the placebo group using:

- For categorical variable: CMH test adjusted by baseline randomization stratification factor [Glucocorticoid use at Baseline ( $\geq 10$  mg/day;  $< 10$  mg/day prednisone equivalent); Length of prior glucocorticoid treatment for PMR ( $\leq 1$  year;  $> 1$  year)].
- For analyses of glucocorticoid dose: ANCOVA mentioned in Section 9.2.

The attributes of the estimands corresponding to the secondary efficacy endpoints are summarized in Table 2.

**Table 2. Summary of the Estimand Attributes of the Secondary Efficacy Endpoints**

For binary endpoint:

Estimand Label	Attributes of the Estimand				Statistical Summary
	Treatment	Endpoint	Population	Handling of Intercurrent Events	
Binary Secondary Variable (Composite)	ABBV-154 vs. Placebo	Achievement of flare-free state up to Week 24	ITT	IE1: Initiation of rescue medication IE2: Initiation of immunomodulator IE3: Initiation of violation of protocol-allowed systemic glucocorticoid use  Subjects will be considered as non-responders for visits after ICEs.	Difference in proportion of subjects achieving flare-free state up to Week 24

For analyses of glucocorticoid dose:

Estimand Label	Attributes of the Estimand				Statistical Summary
	Treatment	Endpoint	Population	Handling of Intercurrent Events	
Analyses of glucocorticoid dose (Treatment Policy)	ABBV-154 vs Placebo	Change from Baseline at Week 24 or cumulative assessment by Week 24	ITT	No IE.	Difference in the mean change from Baseline at Week 24 or cumulative assessment by Week 24

